The Hunter has been very fortunate that collaboration with the Australian Institute of Neuro-rehabilitation (AIN) has procured the purchase of a REX exoskeleton (HELLEN: Hunter’s Exoskeleton for Lower Limb Exercises and Neuro-rehabilitation) and motor vehicle for transport, through a donation from the Newcastle Permanent Charitable Foundation. This is the first purchase of this robotic device in Australia.

There is, to date, no published clinical research evaluating the use of the REX Bionics exoskeleton in patients with MS. The vast majority of anecdotal evidence is also in relation to the use of the REX with spinal cord injured patients. Therefore, there is a need for independent research to establish the feasibility, acceptability and efficacy of lower limb robotics as a potential rehabilitation modality in the MS population.

We anticipate that this pilot study will provide the preliminary data required about safety, feasibility and effect size estimates, which is necessary for progression to a larger randomised trial, if warranted. The results of this trial will complement those from the clinical trial currently underway by this research team investigating the merit of this robotic exoskeleton in the Acquired Brain Injured population.

Objectives

The aim of this project is to examine the potential benefits and applicability of using HELLEN as an adjunct tool for neurorehabilitation in MS, as well as highlighting any barriers and risks to its potential use in this population. It is anticipated that this pilot data will assist in establishing priorities and directing further research in this field.

Trial Design

A phase 1 pre-post intervention trial with 12 week baseline control. This study design has the advantage of allowing all recruits in the study to receive the robotic exercise intervention. We aim to recruit 20 participants in this first stage pilot trial.

Study Setting

The trial will operate at one site only, at the University of Newcastle. A research room has been purpose built for this research in the Hunter Building with designated parking space for participants.

Eligibility Criteria

Inclusion Criteria:

1. Diagnosis of MS
2. Resident of the Hunter region over the age of 18 years
3. Severe mobility impairment whereby the participant is reliant on a mobility aid or other people for upright activities (Scores >6 on the Expanded Disability Status Scale)

Exclusion Criteria

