1. Weight >100kg or <40kg; height >6'4" or <4'8" (criteria set by the REX Bionics)
2. Pregnancy
3. Unstable or severe cardiac or respiratory conditions
4. Recent fractures in lower limbs/pelvis/spine
5. Significant cognitive impairment (<19 on MoCA)
6. Any medical condition which limits the ability to exercise in an upright position

The treatment will only be delivered by REX trained Physiotherapists. Researchers, [name] and [name] have both completed the full 3 day training course and attained competency accreditation.

Intervention

The intervention will involve 2 sessions of exercise therapy per week for 12 weeks. Each session will be up to 1 hour duration and will consist of half an hour of individualised therapy, prescribed and administered by a physiotherapist, including upright weight-bearing exercise facilitated by HELLEN as tolerated by the patient. This may be a combination of sit to stand practise, standing tolerance, weight shift, trunk control exercises, stepping practise, side stepping, squats, upper limb exercises and gait practise. These exercises will be individually tailored to meet the abilities and needs of the client. Participants will also be provided with a home exercise program

relevant to their treatment, which will be assessed and updated throughout the trial as required.

Interventions will only be progressed according to the individual participants' abilities as deemed appropriate by the administering physiotherapist. Interventions will be modified or ceased if, in communication with the participant, the researchers deem that this is necessary.

Outcomes

The timepoints for assessment of outcome measures are:

Week 0: Assessment and assignment to waiting list

Week 12: Commencement of therapy phase

Week 18: Mid- therapy assessment phase

Week 24: End of therapy phase

Week 36: Follow-up phase, 12 weeks after completion of intervention

Participants will be screened for eligibility and baseline measurements will be taken before participants are assigned to a 12 week waitlist. The primary outcome of interest is functional ability as measured by the Motor Assessment Scale. Secondary outcomes include a range of impairment, mood, fitness, and quality of life measures as listed below:

All assessment forms are attached and include:

1. Medical screening form: to determine eligibility for exercise and suitability of the robotic device

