2. Demographic information: Standard demographic and MS information including Kurtzke Expanded Disability Status Scale (EDSS)
3. Cognitive screen MoCA
4. Mood HADS
5. Attitude towards robotic therapy questionnaire
6. Routine physiotherapy assessments using standardised outcome tools: fatigue (FAS), function (MAS and sit to stand test), spasticity (Tardieu), quality of life (SF8), balance (functional reach), independence (Barthel Index), fitness (O2 consumption using the Cosmed K5) strength (dynamometer).
7. Those agreeing to exercise/O2 consumption testing will be assessed wearing the Cosmed K5 O2 mask. During their 3rd or 4th treatment session in HELLEN the participants will be assessed wearing the Cosmed K5 mask, during their 30 minute treatment session in HELLEN. This testing will be repeated during their final HELLEN treatment session.
8. Bioelectrical Impedance Analysis to assess changes in body composition.

Participant Timeline

Potential participants will be identified on the MS database by research nurse, [name]. She will then make telephone contact with potential participants to inform them

of the research and gauge their interest in participating. Those interested, will be provided with an information statement detailing the study and will be contacted by [name], in the following week by phone, to answer any questions they may have and if still interested, to arrange a convenient time for an assessment. Once they are deemed eligible, baseline measures will be collected and they will be placed on a 12 week waitlist. These measures will be repeated after the 12 week period, after 6 weeks of intervention, at the conclusion of 6 weeks of intervention and 12-weeks after the intervention period. After the wait period, twice weekly sessions will continue for 12 weeks. They will then be provided with an ongoing home exercise program. In total, participants will be enrolled in the study for 36 weeks.

Sample Size

20 participants with MS will be invited to participate in this pilot trial.

Recruitment

Potential participants will be identified by [name] via the database maintained by the Newcastle MS clinic, MS Base.

Data Collection Methods

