Data will be collected by [name] in the Physiotherapy Robotics Laboratory (HE14) at the University of Newcastle. Outcome measures will be collected at the beginning of the waitlist phase, the commencement of the trial phase, 6 weeks into the intervention phase, at the end of the intervention (12 weeks), and at the 12 week follow up appointment. The outcome measures have been attached. They have been chosen to reflect a variety of expected benefits of the intervention, and the range of impairments experienced by people with MS.

As the intervention is at no cost to the participants, and offers a type of treatment not currently available to MS patients, there is inherent motivation for the participants to maintain their continued participation in the trial, until the completion of the follow up. For any participants who are lost to follow-up, their last measurements will be imputed into the data and analysed according to intention to treat principles.

Data Management

All data collected from individuals will be maintained in a de-identified form. The data records will be coded using alphanumeric coding to differentiate individual subjects for purposes of analysis. The key for the code will be stored separately on a password protected personal computer. This coding process will be final and subjects will not be re-identified unless they wish to be removed from the study in which case their data will be re-identified, removed from analysis, and destroyed.

Paper copies of clinical measures will contain identifying information about each participant – these will be kept in a separate locked filing cabinet, within the chief investigator's office. Identifying information (names, addresses and contact details)

will not be kept on any database or computer file from the creation of these data files. The data will be coded using an alphanumerical system and the code sheet will be kept in a password protected file on the researcher's computer. Databases will be kept on secured networks (accessible only via password to the researchers named on this application) and hard drive back-up copies will be kept in the same locked filing cabinet as the paper data.

Video files will be downloaded onto the researcher's password protected computer, and deleted from the camera.

All data and findings will be kept for 5 years, consistent with criteria for scientific fraud issues. After that time, all data will be disposed of by shredding or electronic deletion.

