In the event that principle investigator [name] ceases to be engaged with the University of Newcastle, [name] will assume responsibility for the study data.

Statistics

The data collection phase of the trial is expected to take a year. Descriptive statistics, including means and standard deviations (SD), will be calculated for demographic and outcome data. Change scores for each outcome from baseline will be tested using independent t tests for continuous variables and χ^2 tests for categorical variables. Differences from enrolment, baseline, post intervention and 12-week follow up will be evaluated for statistical significance. All analyses will be conducted on an intention-to-treat basis, with missing follow-up data conservatively imputed using the last observation carried forward method. All statistical analysis will be conducted by a qualified statistician.

Descriptive statistics, including means and standard deviations, will be calculated for demographic data. A linear mixed model will be used to detect a significant difference between outcome scores during each time period. The value of the baseline score at the start of the trial and after intervention will be used as a covariate, and analysis conducted to correct for differences in baseline scores and to ensure there is no effect of order. All analyses will be conducted on an intention to treat basis, with missing follow-up data conservatively imputed using the last observation carried forward method.

Data Monitoring

This is a pilot study. No formal interim analysis or DMC is required.

This study will be internally monitored. Chief investigators [name], [name] and [name] will be responsible for ensuring treatment application, data collection, analysis and statistical evaluation are all conducted within accepted scientific practices. Patients will be monitored carefully during the administration of the treatment and adverse events will be documented and submitted to the HREC for evaluation.

Harms

Adverse events will be immediately reported to the ethics committee.

Research Ethics Approval

Application for ethics approval has been given by the Hunter New England Human Research Ethics Committee (17/08/16/4.02).

Protocol Amendments

Protocol amendments affecting future participants will be communicated via a revised participant information form. The research protocol, where necessary, will be revised and disseminated to all relevant parties.

Informed Consent

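### The independent t tests and chi-square tests named for change scores do not fit a single cohort measured repeatedly, and they stand unreconciled beside the planned mixed model

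*Protocol*

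**What the plan says.** Trial Design describes a pre-post trial with a 12-week baseline control and no parallel arm: "This study design has the advantage of allowing all recruits in the study to receive the robotic exercise intervention". Sample Size gives "20 participants with MS will be invited to participate in this pilot trial". Outcomes lists assessments of the same people at weeks 0, 12, 18, 24 and 36, and states "The primary outcome of interest is functional ability as measured by the Motor Assessment Scale".

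The first paragraph of Statistics says "Change scores for each outcome from baseline will be tested using independent t tests for continuous variables" and adds chi-square "tests for categorical variables". It then lists enrolment, baseline, post-intervention and 12-week follow-up as the points between which differences will be tested.

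The second paragraph says "A linear mixed model will be used to detect a significant difference between outcome scores during each time period". It lists the score at the start of the trial and the score after the intervention as covariates. It does not say how this model relates to the t tests.

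**The concern.** An independent t test needs two samples of different people. This trial has none. Any two samples that could be formed (two visits, or two change scores) come from the same participants. The test therefore leaves out the covariance between them, and its standard error is wrong whenever that covariance is not zero. A chi-square test of visit by response has the same fault, because each participant is counted once per visit.

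The sentence covers each outcome, so it includes the Motor Assessment Scale. For categorical outcomes, chi-square is the only test named.

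The Protocol commits to significance testing. Its Background section says that the pilot is to supply effect-size estimates for deciding on a larger randomised trial. A misstated standard error would not move the mean change, but it would misstate how precisely that change is known.

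**Working it through.** The Protocol gives no power, effect size, SD or correlation, so it has no figure to reproduce.

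**Inputs.** From the Protocol: n = 20, one cohort, the same people at each visit. Assumed: normal data, equal variance at each visit, complete data, two-sided 5% tests, and correlation r from 0.3 to 0.9 between visits. Correlation is taken either as equal for all pairs of visits or as AR(1), with r between visits 12 weeks apart and r² between weeks 0 and 24. Simulated values for continuous scores use 40,000 trials per setting unless stated.

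**(a) Visit against visit (for example week 12 against week 24).** The independent test assumes variance 2σ²/n for the mean difference. The true variance is 2σ²(1 − r)/n. The standard error is too large by 1/√(1 − r). Take an effect of 0.66 SD of the change, which the paired test detects with 80% power at n = 20. In units of the visit SD this is 0.66 × √(2(1 − r)).

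| r | SE ratio | Effect, visit SDs | Power, independent | Power, paired |
|---|---|---|---|---|
| 0.3 | 1.20 | 0.78 | 70% | 80% |
| 0.5 | 1.41 | 0.66 | 54% | 80% |
| 0.7 | 1.83 | 0.51 | 26% | 80% |
| 0.9 | 3.16 | 0.30 | under 1% | 80% |

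With no effect, the independent test rejects in 2.1% (r = 0.3), 0.7% (0.5) and 0.1% (0.7) of trials, and almost never at 0.9 (100,000 trials).

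**(b) Two changes from week 0 (week 12 minus 0, week 24 minus 0).** The true variance of their difference is that of week 24 minus week 12, which is 2σ²(1 − r) per person.
- Equal correlation: the independent test assumes 4σ²(1 − r). The SE ratio is √2, and 2(1 − Φ(1.96 × 1.414)) is about 0.6%. Simulation with t tests gives 0.7 to 0.8%.
- AR(1): the SE ratio is √(2 + r), from 1.52 (r = 0.3) to 1.70 (r = 0.9). Simulation gives 0.5% down to 0.2%.

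**(c) Wait-period change against therapy-period change (week 12 minus 0, week 24 minus 12).** The week-12 score enters the two changes with opposite signs, so they correlate negatively and the independent standard error is too small.
- Equal correlation: the two changes correlate at −0.5 for every r. Type I error is 2(1 − Φ(1.96 × √(2/3))) = 2(1 − Φ(1.60)) = 11.0%. Simulation gives 10.7 to 11.0%.
- AR(1): the two changes correlate at −(1 − r)/2, that is −0.35 at r = 0.3 and −0.05 at r = 0.9. Simulation gives 9.1% falling to 5.6%.
- The paired test on the same contrast stays at about 5% throughout.

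**(d) Chi-square on paired binary data.** With 20 people, response probability 0.5 at both visits and within-person correlation φ, type I error is 4.2% (φ = 0), 1.6% (0.3), 0.6% (0.5) and 0.05% (0.7) in 100,000 trials.

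**The case against.** **The mixed model.** The strongest reply is that the second paragraph of Statistics already plans a model that can account for within-person correlation, including for the Motor Assessment Scale if that is treated as continuous. This stands. A reader might infer that every p-value in the trial, including the primary one, will be wrong. The document does not support that: the defect is confined to the independent t tests and the chi-square tests. The model does not repair the sentence, however. It does not replace the t tests, it does not serve categorical outcomes, and its covariates as worded include the score after the intervention.

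**The contrast.** The Protocol does not say which two sets of change scores the t test would compare. Outcomes uses the word baseline for the measurements before the waitlist, while Statistics lists enrolment and baseline separately. A reader might infer that the plan inflates type I error to 11%. That needs contrast (c) and equal correlation, and the Protocol states neither. Contrast (b) errs in the opposite direction. This objection also stands.

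**The scale of the power loss.** In (a) the effect in visit SDs shrinks as r rises, which contributes to the fall below 1%. With the effect fixed at 0.5 visit SD, independent-test power is 31% (r = 0.3), 29% (0.5), 25% (0.7) and 17% (0.9), against 44%, 57%, 78% and 99.7% for the paired test. The loss is smaller at high r on this scale but remains substantial.

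**Pilot status.** No decision rule rests on a p-value, and mean changes are the same under either t test. This limits the harm but does not make the named test correct.

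**Selective reporting.** A reader might infer that two unranked analyses invite a choice of the favourable one. Nothing in the Protocol shows that intent, and the ranking may be set in a statistical analysis plan that is not shown.

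**Conclusion.** The sentence is wrong as written. P-values from independent t tests and chi-square tests are invalid here whenever a participant's measurements are correlated, and the Protocol offers no pair of independent samples to which the tests could apply. The conclusion about fit follows from the design alone and needs no assumption about r.

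Its size and direction are conditional. The tests are conservative for visit against visit and for two changes from week 0. They are anti-conservative for wait-period against therapy-period change, mildly so under AR(1) with high r. The figures assume 20 complete participants, normal scores and the stated correlation range. A properly specified mixed model for continuous outcomes is outside the criticism.

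**What to change.** 1. Delete the sentence on independent t tests and chi-square tests. If simple tests are wanted in support, replace it with the paired t test or Wilcoxon signed-rank test for continuous or ordinal scores, and exact McNemar for paired binary outcomes.
2. Name the linear mixed model as the main analysis of the Motor Assessment Scale, with visit as a categorical fixed effect and within-participant correlation modelled. A participant random effect would do this. Alone it imposes equal correlation between visits, so a less restrictive covariance is an alternative.
3. Name its main contrast, for example therapy-period change minus wait-period change, and say which visit baseline means.
4. Remove the score after the intervention from the covariates. It is part of the outcome, and adjusting for it could remove the effect sought.

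The cost is wording in the Statistics section and minor analysis work. No new data are needed.

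### Baseline denotes two different visits, and no stated analysis compares change over therapy with change over the 12-week wait, the comparison that would use the design's control

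*Protocol*

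**What the plan says.** The title and the Trial Design section describe the study as "A phase 1 pre-post intervention trial with 12 week baseline control". There is one group, and each participant waits 12 weeks before therapy. The Outcomes section schedules assessments at Weeks 0, 12, 18, 24 and 36 and names the Motor Assessment Scale as primary.

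Baseline is used as follows:

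- Outcomes: "baseline measurements will be taken before participants are assigned to a 12 week waitlist". This is Week 0.
- Participant Timeline: "baseline measures will be collected and they will be placed on a 12 week waitlist". Again Week 0.
- Outcomes, visit list: "Week 12: Commencement of therapy phase". This visit is not called baseline.
- Statistics: "Differences from enrolment, baseline, post intervention and 12-week follow up will be evaluated for statistical significance". Enrolment and baseline are now separate, and baseline comes before the post-intervention visit.

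The Statistics section commits to three kinds of comparison. The first is a test of change: "Change scores for each outcome from baseline will be tested using independent t tests for continuous variables". The second is the set of visit differences just quoted. The third is a model: "A linear mixed model will be used to detect a significant difference between outcome scores during each time period". The Sample Size section gives the number without a power basis: "20 participants with MS will be invited to participate in this pilot trial".

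**The concern.** A waiting period works as a control only if what happens during therapy is set against what happened during the wait. Disease trend, practice on the tests or general improvement from being followed can move scores in both periods. A change from Week 12 to Week 24 includes whatever drift occurs in those 12 weeks. A change from Week 0 to Week 24 includes twice as much if the drift is steady. Finding the therapy change significant and the wait change not significant does not test whether they differ.

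With baseline attached to two visits, two analysts following the same text could report different primary results. The Background section says the pilot is to supply effect size estimates for a possible larger randomised trial. An estimate that depends on which visit is called baseline, and that absorbs drift, could mislead the planning of that trial.

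**Working it through.** **Which visit is baseline.** In Outcomes and Participant Timeline the baseline measures come before the wait, so they are Week 0. In the four-visit list in Statistics, enrolment is the Week 0 visit, and the remaining pre-therapy visit is Week 12. The same section also mentions a baseline score at the start of the trial, while Data Collection Methods refers to Week 12 as the start of the trial phase. The text therefore supports both readings.

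**Inputs.** The protocol states no alpha, SD, correlation, drift or effect size, so there is no figure of its own to reproduce. From the protocol: n = 20 and visits at Weeks 0, 12 and 24. Assumed: two-sided 5% level, equal SD at each visit (set to 1), common within-person correlation rho of 0.5 to 0.9, steady drift d of 0.1 or 0.2 SD per 12 weeks, and no HELLEN effect.

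**Simple changes, paired test.** The variance of a change between two visits is 2(1 - rho). The noncentrality on 19 degrees of freedom is

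- Week 24 against Week 12: d x sqrt(20) / sqrt(2(1 - rho))
- Week 24 against Week 0: 2d x sqrt(20) / sqrt(2(1 - rho))

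Example with d = 0.2 and rho = 0.7: 0.2 x 4.472 / 0.775 = 1.15 and 0.4 x 4.472 / 0.775 = 2.31. The noncentral t distribution then gives rejection in 19.5% and 59.2% of trials.

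| Drift per 12 weeks | rho | Week 24 v Week 12 | Week 24 v Week 0 |
|---|---|---|---|
| 0.1 SD | 0.5 | 7.1% | 13.6% |
| 0.1 SD | 0.7 | 8.5% | 19.5% |
| 0.1 SD | 0.9 | 15.8% | 47.6% |
| 0.2 SD | 0.5 | 13.6% | 39.7% |
| 0.2 SD | 0.7 | 19.5% | 59.2% |
| 0.2 SD | 0.9 | 47.6% | 96.6% |

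**Difference of the two changes.** (Week 24 - Week 12) - (Week 12 - Week 0) = Week 24 - 2 x Week 12 + Week 0. Under linear drift its mean is 0, so a within-person test keeps its 5% level (simulated 4.9% to 5.3%, 20,000 runs per setting). Its variance is 6(1 - rho), against 2(1 - rho) for a simple change, so its standard error is sqrt(3) = 1.73 times as large. At rho = 0.8 and n = 20 the 95% half-widths are 2.093 x sqrt(0.4/20) = 0.30 SD for the simple change and 2.093 x sqrt(1.2/20) = 0.51 SD for the contrast. Effects detectable with 80% power at rho = 0.5, 0.7 and 0.9 are 0.66, 0.51 and 0.30 SD for the simple change, and 1.14, 0.89 and 0.51 SD for the contrast.

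**The independent t test as worded.** If it is applied to the two periods' change scores, it treats them as unrelated. Both contain the Week 12 value, and their correlation is -(1 - rho) / (2(1 - rho)) = -0.5. The test assumes a variance of 4(1 - rho)/n for the difference where the true value is 6(1 - rho)/n. Simulation gives about 11% rejection when the two periods do not differ. If it is applied to raw scores at rho = 0.7, it ignores the pairing: rejection is about 0.1% with no drift, and at 0.2 SD drift 1.3% for Week 24 v Week 12 and 11% for Week 24 v Week 0.

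**Drift that is not linear.** Suppose a single re-test gain of 0.2 SD by Week 12 and none after. The contrast then has mean -0.2 SD, and it rejects in 10%, 12% and 20% of trials at rho = 0.7, 0.8 and 0.9, in the direction against HELLEN. Week 24 against Week 12 keeps its 5% level in that case.

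**The case against.** Several points on the other side are good.

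- A reader might infer that the control period enters no comparison at all. The text does not support that: enrolment and baseline are both in the list of visit differences, so change over the wait can be tested.
- A reader might infer that the trial is unable to separate an exoskeleton effect from drift. That also goes too far. Weeks 0, 12 and 24 are collected, and a mixed model fitted to them can give the contrast. The model sentence mentions time periods and could be read as a comparison of periods, although it speaks of scores, not changes.
- In a one-group trial, the independent t test on change scores may have been meant to compare the wait with therapy. If so, the intention is right, but the test is wrong for it, as the 11% shows.
- A reader might take the visit list to mean every pair of visits on every outcome and count the false positives to be expected. The text does not say this. Handling of multiplicity is commonly left to an SAP, and a primary outcome is named.
- The rejection rates model a paired test, not the literal independent test, which on raw scores rejects far less often. They apply to a within-person visit comparison such as the mixed model would give.
- Exact model contrasts may also sit in an SAP that is not at hand.

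What remains is in the current protocol text: baseline is placed at two visits, and the stated tests do not include the comparison for which the design is named. An SAP could not resolve the first without overriding one of the sections.

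**Conclusion.** The concern holds in a limited form and should be fixed. Baseline is Week 0 in two sections and, by implication, Week 12 in Statistics. The waiting period is listed among the visit differences, but no stated analysis compares change over therapy with change over the wait. Followed as written, change-from-baseline tests would credit steady drift to HELLEN, or subtract it, and the size of that error depends strongly on which visit is taken as baseline. The inflated rejection rates rest on assumed drift, assumed correlation and a paired test; they illustrate the size and are not predictions. This is a 20-person pilot and the data needed are already scheduled, so the defect lies in the specification and not in the design.

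**What to change.** Refer to visits by week throughout and define baseline once. In Statistics, name one main contrast for the Motor Assessment Scale, estimated within person in the mixed model: (Week 24 - Week 12) - (Week 12 - Week 0), with a 95% CI. Report the two component changes beside it. Remove the independent t test on change scores, or replace it with this within-person comparison.

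The change is to wording only; no visit or measurement is added. Its statistical costs should be stated in the protocol. Under compound symmetry the standard error is sqrt(3) times that of the simple change, so with 20 participants the result is best presented as an estimate with its interval. The contrast removes linear drift only. A one-off re-test gain biases it against HELLEN, and expectation that begins with therapy is not removed. Showing both component changes lets a reader judge these possibilities.

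### Last observation carried forward is not reliably conservative in this single-group design, and it overstates Week 36 benefit if gains wane after device sessions stop

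*Protocol*

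**What the plan says.** The rule appears three times in the protocol.

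- Data Collection Methods: for anyone lost to follow-up, "their last measurements will be imputed into the data and analysed according to intention to treat principles".
- Statistics, first paragraph, after the change-score tests: all analyses are by intention to treat, with "missing follow-up data conservatively imputed using the last observation carried forward method".
- Statistics, second paragraph: the same rule in the same terms, directly after "A linear mixed model will be used to detect a significant difference between outcome scores during each time period".

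The design (Trial Design) is "A phase 1 pre-post intervention trial with 12 week baseline control", so there is no concurrent arm. The Outcomes section sets the visits. Those that matter most here are "Week 12: Commencement of therapy phase", the end of therapy at Week 24, and "Week 36: Follow-up phase, 12 weeks after completion of intervention". Under Statistics, "Differences from enrolment, baseline, post intervention and 12-week follow up will be evaluated for statistical significance", so Week 36 is a tested comparison.

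The protocol gives no reason for calling the method conservative. It also gives no expected dropout, no expected course after Week 24, and no sensitivity analysis. Participant Timeline says that home exercise goes on after the sessions end.

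**The concern.** Carrying a score forward assumes that the participant stays exactly as last seen. Whether that is cautious depends on which visit is copied and where.

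For someone lost after Week 24, the copied score is the one taken at the end of therapy, and it fills the visit meant to show what remains 12 weeks later. That assumes full retention. For someone who leaves because they are worsening, the worsening disappears. With one group and no concurrent arm, nothing offsets either error.

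The rule is also unnecessary for the planned model. A linear mixed model can use incomplete records as they stand. Filling the gaps first means that copied values are analysed as if they had been measured.

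At stake are the Week 36 comparison and the effect size estimates that Background and Rationale expects this pilot to hand to a larger randomised trial.

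**Working it through.** **Inputs from the protocol.** 20 participants; therapy from Week 12 to Week 24; follow-up at Week 36; LOCF for all analyses. The protocol has no figure of its own on this point to reproduce.

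**Assumptions, not in the protocol.** Loss of 10, 20 or 30%; a Week 24 gain of 0.5 SD; a wait-period change of −0.1 SD; correlation 0.8 between visits; two-sided 5% test. The check uses a paired t test because the same people give both scores. The protocol names independent t tests, which is a separate matter.

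**Step 1. Week 36 minus Week 12, dropouts last seen at Week 24.** For a loss *d* unrelated to outcome:

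LOCF mean = (1 − d) × true Week 36 change + d × Week 24 change

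With 20% loss and a 0.5 SD gain fully gone: 0.8 × 0 + 0.2 × 0.5 = 0.10 SD.

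| Course after a 0.5 SD gain | True | LOCF, 10% loss | LOCF, 20% loss | LOCF, 30% loss |
|---|---|---|---|---|
| Fully kept | 0.50 | 0.50 | 0.50 | 0.50 |
| Half kept | 0.25 | 0.275 | 0.30 | 0.325 |
| Fully lost | 0.00 | 0.05 | 0.10 | 0.15 |
| 0.1 SD below the start | −0.10 | −0.04 | +0.02 | +0.08 |

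In the last row, the sign of the estimate has changed at 20% loss.

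**Step 2. False findings of retained benefit when the gain is fully lost.** Simulation with n = 20 and 40,000 trials per case; the nominal upper-tail rate is 2.5%.

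| Loss | 10% | 20% | 30% |
|---|---|---|---|
| At random | 5.3% | 9.2% | 15.5% |
| At random, exactly 2, 4 or 6 of 20 (separate run) | 4.8% | 8.3% | 14.2% |
| Those with the worst change after Week 24 are lost | 14% | 37% | 63% |

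**Step 3. Earlier loss.**

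- Week 24 minus Week 12, dropouts last seen at Week 12: LOCF mean = (1 − d) × true change. A true +0.5 becomes 0.45, 0.40 or 0.35, which understates the gain. A true −0.1 becomes −0.09, −0.08 or −0.07, which hides part of the decline.
- Therapy change minus wait change, dropouts last seen at Week 0: the true contrast is 0.5 − (−0.1) = 0.60, and LOCF gives 0.54, 0.48 or 0.42.

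**Step 4. No imputation.** In the fully lost case of Step 1, a likelihood-type estimate that predicts Week 36 from Weeks 12 and 24 among those observed averages about 0.00 SD at each loss rate (4,000 trials). LOCF gives 0.05, 0.10 and 0.15.

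**Step 5. A case where loss is not at random.** Suppose that 16 gain 1 point, and 4 stop for poor tolerance, were last seen at Week 12, and would have lost 1 point.

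- Truth: (16 × 1 − 4 × 1)/20 = 0.6
- LOCF: (16 × 1 + 4 × 0)/20 = 0.8
- Observed data under missing at random: about 16/16 = 1.0, if earlier scores do not predict the change

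Both methods are optimistic here, and the analysis without imputation more so.

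**The case against.** A reader might infer that LOCF favours the device throughout. The documents do not support that. The Week 36 bias needs scores to fall after Week 24. The protocol states no such course, and home exercise continues. Step 3 shows that earlier loss can work against the device.

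A reader might also infer that LOCF only adds bias and that dropping it cures the problem. Step 5 refutes this. When people leave because they do badly, an analysis that assumes missing at random can be further from the truth.

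Nor does LOCF shrink the SD of change as a rule. With 4 of 20 records set to zero change, the variance is 0.8s² + 0.16m², where *m* and *s* are the mean and SD of true change. The SD falls by 1 − √0.8, about 11%, only when m = 0. At m = 0.79s (a 0.5 SD gain with correlation 0.8) it falls by about 5%, and above m = 1.12s it rises. At Week 36 the copied value is not zero change. If the group is 0.5 SD above its Week 12 level at Week 24 and 0.1 SD above at Week 36, 20% loss raises the SD from √0.4 = 0.632 to √(0.4 + 0.16 × 0.4²) = 0.652.

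The strongest point on the other side is size. In that same case the bias is 0.2 × (0.5 − 0.1) = 0.08 SD, below the standard error of about 0.632/√20 = 0.14 SD, and 95% interval coverage is still about 92%. Data Collection Methods also expects motivated participants to stay, though it gives no rate. Week 36 is one of several tested time points, and the protocol makes no separate claim of retention.

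All of this limits the severity. It does not rescue the label: a method whose direction is unknown in advance cannot be called conservative.

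**Conclusion.** The point holds in a limited form. The protocol fixes LOCF as the main method for all analyses, including a model that does not need it, and gives it a direction that it does not reliably have. It overstates retained benefit at Week 36 if gains wane, hides decline in dropouts who worsen, shrinks true gains when loss comes earlier, and does no harm at Week 36 if gains are kept.

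At 20% loss with a 0.5 SD gain fully gone, the error is +0.10 SD with about 8–9% one-sided false positives. Every such figure rests on assumed dropout and waning and is not an estimate for this trial. The redundancy with the mixed model rests on no such assumption. This should be fixed. It is not severe enough to put the trial in doubt.

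**What to change.** - In Data Collection Methods and in both paragraphs of Statistics, delete LOCF as the main method and delete the word conservatively.
- State that the linear mixed model is fitted by REML to all observed visits without imputation, and that this is valid under missing at random.
- Add one sensitivity analysis in which dropouts have worse outcomes, for example a delta shift or a return to the Week 12 score at Week 36. Step 5 shows why this is needed alongside the main analysis.
- Keep LOCF, if at all, as a labelled secondary sensitivity analysis.

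The cost is a few sentences in two sections, slightly wider intervals, and a little more analysis work.
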